3.5.2 EORTC QLQ-STO22 and Analysis of EORTC QLQ-STO22

The EORTC QLQ-STO22, a disease-specific 22-item self-administered questionnaire for gastric cancer ([Vickery et al, 2001](#)), was developed to be used in conjunction with the EORTC QLQ-C30 v3.0. The scoring of the symptom scales/items will follow the EORTC scoring algorithm. For the symptom scales and items a higher score is equivalent to worse or more symptoms. In the functional scales, a high score is equivalent to better function.

Time to deterioration analysis will be conducted in the same for the following symptom scales of the EORTC QLQ-STO22 as described for the EORTC QLQ-C30 multiple-item scales: STODYS (dysphagia) score, STOEAT (eating restriction) score, STOPAIN (stomach pain) score, and STOFX (reflux) score. A change of at least 10 points in the score will be considered as a clinically relevant or a minimally important difference.

Change from baseline for each of the summary scales and single item measures described above will be summarized descriptively. Summary symptom scores: STODYS (dysphagia) score, STOEAT (eating restriction) score, STOPAIN (stomach pain) score, and STOFX (reflux) score will be included. Multiple item system scale STOANX (anxiety) and single item measures: STODM (dry mouth) score, STOT (taste) score, STOBI (body image) score, and STOHL (hair loss) score will not be summarized but will be presented in by-subject listings.

Similarly, compliance overall and over time will be summarized by randomized or assigned treatment for the EORTC QLQ-STO-22 questionnaire as was described for the EORTC QLQ-C30.

3.6 Pharmacodynamic Endpoint(s) and Analyses

3.6.1 Pharmacodynamic Endpoint(s)

Exploratory pharmacodynamic endpoints are listed in Section 2.2.3 of the protocol.

3.6.2 Analysis of Pharmacodynamic Endpoint(s)

The pharmacodynamic endpoints will be analyzed by the MedImmune Translational Sciences group or their designee.

3.7 Other Additional Analyses

Not applicable.

3.8 Safety Analyses

In Phase 1b, the number of DLTs that are identified in the DLT Evaluable Population during the DLT evaluation period will be summarized and listed. Safety data including AEs, SAEs, laboratory parameters, ECGs, vital signs and ECOG performance status, will be summarized in the As-treated population by treatment group, pooled dose groups and overall.

Repeated or unscheduled tests will not be summarized for each scheduled visit, but will be included for summaries of “worst-case” on treatment values and shift-table analyses. “Worst-case” on treatment (i.e. maximum or minimum on-treatment value depending on the direction of an adverse effect) is defined as the nadir and/or zenith including any scheduled and unscheduled post-baseline assessments that occur through the last assessment on-treatment. The last assessment on-treatment is defined as the last visit with a non-missing observation that occurred up till 90 days (+7 days to allow for a visit window) following the last dose of study treatment (if safety follow-ups are performed till 90 days after the last dose), or till the initiation of the subsequent anticancer therapy (excluding palliative radiotherapy), whichever occur first.

If the number of subjects with available data is less than 10% of the total number of subjects in the As-treated Population for overall summary for the dose escalation phase, or for each cohort in the dose expansion phase at a scheduled time of evaluation, no summary statistics will be presented at that time point, unless otherwise indicated.

3.8.1 Adverse Events and Serious Adverse Events

Adverse events will be coded using Medical Dictionary for Regulatory Activities and assigned grades based on NCI CTCAE v4.03.

Treatment-emergent adverse event (TEAE) will be defined for the initial treatment period and subsequent treatment periods separately. TEAEs are defined as any adverse events that occur on or after the date of initial receipt of study treatment during each treatment period. Analysis of AEs (as described below) will be limited to TEAEs. Any AEs that are considered as non-treatment emergent will be presented in the listings only.

For both Phase 1b and Phase 2, the number and percentage of subjects reporting treatment-emergent AEs will be summarized overall and by the worst NCI CTCAE v4.03 grade, system organ class, and preferred term. Similarly, the number and percentage of subjects reporting treatment-emergent AEs considered related to investigational product will be summarized. At each level of subject summarization, a subject will be counted once using the highest grade and level of causality if one or more occurrences of the same system organ class/preferred term is reported. SAE will be summarized overall, by system organ class and preferred term, and by SAE criteria. The number and percentage of subjects reporting treatment-emergent SAEs considered related to investigational product will also be summarized.

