1. Confirmed PD: The assessment of PD by RECIST v1.1 (baseline PD assessment) will be confirmed by a repeat evaluation at the next tumor assessment time point, but no sooner than 4 weeks later. If any subsequent tumor assessment time point shows $\geq 20\%$ increase in the overall tumor burden (the sum of diameters of target lesions and new lesions), when compared to the baseline PD assessment (the sum of diameters of target lesions and new lesions), the subject would be deemed as having confirmed PD.
 - a. Note: Subjects in Arm B (MEDI4736 monotherapy) and Arm C (tremelimumab monotherapy) of Phase 2 who experience a confirmed PD (as defined above) will have the option (on a case-by-case basis) to crossover to treatment with MEDI4736 in combination with tremelimumab (using the Phase 2 schedule) for 12 months or until a second confirmed PD. Crossover will be permitted as long as the treatment beyond progression criteria are met and any of the investigational product discontinuation criteria (with the exception of criterion number 10 in Section 4.1.6) are not met. If crossover is not chosen by the investigator, then the study treatment must be discontinued.
 - b. Note: Subjects with confirmed PD during 12 months of treatment with MEDI4736 in combination with tremelimumab (Phase 1b, and Arms A and D, and E of Phase 2) may not crossover to either MEDI4736 monotherapy or tremelimumab monotherapy at any time. Subjects enrolled in Phase 1b, and Arms A, D, and E of Phase 2 who exhibit confirmed PD after completing the planned 4 doses of combination treatment, but prior to completing the 12-month dosing period (ie, while receiving MEDI4736 monotherapy) may be eligible for reinduction (on a case-by-case basis) with combination therapy and continued treatment for an additional 12 months (or until the subject meets any of the discontinuation criteria listed below). The subject would be readministered investigational products according to the same treatment guidelines followed during their initial treatment. Subjects who are enrolled in Phase 1b and Arms A, D, and E of Phase 2 and who exhibit disease progression prior to completing the planned 4 doses of combination treatment may be eligible for continued treatment through the end of the planned 12-month treatment period (or until the subject meets any of the discontinuation criteria listed below), but will not be eligible for reinduction.

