4.8.4.1 Analysis of Adverse Events

In Phase 1b, the number of DLTs that are identified in the DLT Evaluable Population during the DLT evaluation period will be summarized or listed. For both Phase 1b and Phase 2, the number and percentage of subjects reporting treatment-emergent AEs will be summarized overall and by the worst NCI CTCAE v4.03 grade, system organ class, and preferred term, with a breakdown by treatment arm. Similarly, the number and percentage of subjects reporting treatment-emergent AEs considered related to investigational product will be summarized. At each level of subject summarization, a subject will be counted once using the highest grade and level of causality if one or more occurrences of the same system organ class/preferred term is reported. AEs will be graded according to the NCI CTCAE v4.03 and coded using the Medical Dictionary for Regulatory Activities.

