5.4.1 Time Period for Collection of Adverse Events

AEs will be collected from time of signature of informed consent, enrollment, randomization, throughout the treatment period and including the follow-up period of 90 days after the last dose of MEDI4736 and tremelimumab.

SAEs will be recorded from the time of informed consent signature through 90 days after the last dose of MEDI4736 and tremelimumab.

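### Adverse events are shown by arm only as crude percentages, although the time at risk can differ between randomised Arms A, B and C, so side-by-side figures can mislead in either direction

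*SAP*

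**What the plan says.** **Measure.** SAP 3.8.1 states that "the number and percentage of subjects reporting treatment-emergent AEs will be summarized overall and by the worst NCI CTCAE v4.03 grade". Related events, SAEs (3.8.1), AESIs (3.8.2) and events leading to discontinuation or death (3.8.3) are handled in the same style. Protocol 4.8.4.1 adds that the summary comes "with a breakdown by treatment arm". The visible text contains no person-time rate, cumulative incidence or common time point.

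**Window.** Protocol 5.4.1 collects events "throughout the treatment period and including the follow-up period of 90 days after the last dose of MEDI4736 and tremelimumab". SAP 3.8.1 works period by period: "Treatment-emergent adverse event (TEAE) will be defined for the initial treatment period and subsequent treatment periods separately". It then says "TEAEs are defined as any adverse events that occur on or after the date of initial receipt of study treatment during each treatment period": a start, but no end. SAP 3.8 does define an end of the on-treatment interval for worst-case values (90 days plus a 7-day allowance after last dose, or the start of subsequent anticancer therapy). No such end is given for adverse events.

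**What ends the initial period.** Under Protocol 3.1.2.4, subjects in Arms B and C with confirmed PD "will have the option (on a case-by-case basis) to crossover to treatment with MEDI4736 in combination with tremelimumab". Arm A subjects may be reinduced only if PD is confirmed after the 4 combination doses and before month 12. Retreatment during follow-up is possible in every arm. Protocol 4.1.6 stops dosing for an event that meets DLT criteria, inside or outside the DLT evaluation period, and ends protocol assessments when alternative anticancer treatment starts.

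**Related summaries.** SAP 3.3.3 describes duration of exposure and SAP 3.3.1 describes discontinuations with reasons. Neither is linked to the adverse-event tables.

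**The concern.** The chance of at least one event rises with time under observation. If two arms have the same event rate per month but different windows, their crude percentages differ.

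Here the window length is partly an outcome of treatment: later progression lengthens it and toxicity stops shorten it. The per-period definition can also remove the 90-day tail. A subject who crosses over leaves the monotherapy window at that point, while an Arm A subject who progresses before finishing the combination doses cannot be reinduced and keeps the tail.

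Arms A, B and C are randomised, and describing the safety of all three regimens is a Phase 2 secondary objective. Percentages in adjacent columns will be read against each other. An artefact of window length could be taken for a difference in toxicity, or could hide one.

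**Working it through.** **Inputs from the documents**
- PFS-6 of 35% vs 10% for A vs C (SAP 2.4.2).
- Median PFS of 6.6 months, and 4.4 months for the cited comparator (SAP 2.4.2). The 4.4 months serves here as the Arm B scenario; a PFS-6 of 39%, 14 points below 53%, also gives 4.42 months.
- 12-month treatment cap; PD confirmed at least 4 weeks later (Protocol 3.1.2.4).
- 90-day tail (Protocol 5.4.1) = 90/30.4375 = 2.957 months.

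**Assumptions.** Exponential PFS in all arms; event hazard h per month, the same in both arms; crossover fraction x; toxicity-stop rates. The documents give no values for h, x or the stop rates.

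**Reproducing the plan's own figures.** Exponential median = 6·ln2/(−ln PFS-6). For 53% this is 6.55 months and for 24/45 it is 6.62, against the stated 6.6. Pooled power for 35% vs 10% with 45 vs 22 subjects at 1-sided 0.10 is 0.858, against the stated 85%.

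**Simplest model: dosing stops at PD, no crossover.** Mean window = (1 − e^(−12λ))/λ + 2.957, with λ = −ln(PFS-6)/6.
- A: λ = 0.1750; (1 − 0.1225)/0.1750 + 2.957 = 7.97 months.
- C: λ = 0.3838; (1 − 0.01)/0.3838 + 2.957 = 5.54 months.

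Crude proportion = 1 − e^(−2.957h)·[λ + h·e^(−12(λ+h))]/(λ+h). At h = 0.05:
- A: 1 − 0.8626 × 0.7927 = 31.6%.
- C: 1 − 0.8626 × 0.8854 = 23.6%.

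The gap is 8.0 points with identical hazards.

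**Dosing to confirmed PD.** Window = min(PFS + 28 days, 12 months) + 90 days, with the tail dropped for those who cross over. Crude proportion = 1 − E[e^(−h·window)]. Differences are in points, Arm A minus comparator:

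| Scenario | Crossover | Mean window (months) | h = 0.02 | h = 0.05 | h = 0.10 |
|---|---|---|---|---|---|
| A vs B (medians 6.6, 4.4) | 0% | 10.4 vs 9.1 | 2.1 | 3.9 | 4.8 |
| A vs B | 50% | 10.4 vs 7.9 | 4.3 | 8.4 | 11.6 |
| A vs C (medians 3.96, 1.81) | 0% | 8.8 vs 6.4 | 3.9 | 7.4 | 9.5 |
| A vs C | 50% | 8.8 vs 5.0 | 6.5 | 13.1 | 18.7 |
| Equal medians (4.4, 4.4) | 50% | 9.1 vs 7.9 | 2.2 | 4.5 | 6.7 |

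The last row shows that the cut at crossover is enough to open a gap with no difference in PFS.

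**What shrinks or reverses it**
- Front-loaded events (hazard 80% lower after month 4, initial h = 0.05): A vs B +1.0 at 0% crossover and +3.1 at 50%; A vs C +1.8 and +5.2.
- Reinduction cutting Arm A's tail for 50%, as crossover does for 50% of B, h = 0.05: 35.8% vs 31.0%, so the A vs B gap falls from 8.4 to 4.8.
- Toxicity stops in Arm A only, no crossover in B, h = 0.05: at 0.03/month, 36.4% vs 35.5%; at 0.05/month, 34.7% vs 35.5%; at 0.10/month, 31.3% vs 35.5% (mean windows 7.8 vs 9.1). The sign reverses although A has the longer PFS.

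**Which summary repairs it.** Take A vs C in the simplest model with hazard 0.15/month to month 3, then 0.03, equal in both arms.
- Crude: 44.7% vs 40.7%.
- First events per person-month: 0.085 vs 0.104, ratio 0.82. The combination looks 18% safer when it is not.
- 3-month cumulative incidence: both arms return 1 − e^(−0.45) = 36.2%, to within 0.1 point.

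The 3-month estimate works because the 90-day tail alone keeps nearly every subject at risk for 3 months, apart from death, a new treatment period or new therapy.

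**The case against.** **A reader might infer that the window is always longer in the arm with longer PFS, so the combination will look too toxic.** The documents do not support this as a feature of the design. Dosing continues past first PD, is capped at 12 months and is stopped by DLT-type events; follow-up can end at new therapy. The toxicity-stop figures show that the direction can reverse. It is therefore unknown in advance.

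**A reader might infer that a planned safety comparison is biased.** None is planned. The objective is to describe safety, and between-arm comparisons are specified only for ORR and PFS-6. The point concerns how descriptive tables are read.

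**The period cut is not confined to B and C, and it is sound attribution.** Both parts stand. Reinduction and retreatment can cut Arm A's window, although reinduction is more restricted than crossover. Events after crossover occur on the combination and should not be charged to monotherapy. What needs repair is the unequal time at risk that results.

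**Noise is larger than the artefact.** This largely stands. With 45 per arm and 40% incidence the standard error of a difference is √(2 × 0.24/45) = 10.3 points. Protocol 3.1.1 reports 89 subjects in Arms A to D; if Arm D reached its planned 25, about 26/26/13 remain in A/B/C, giving about 14 points (A vs B) and 17 (A vs C). That limits the weight any comparison can carry, but an avoidable distortion still adds to the noise.

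**The imbalance is visible elsewhere.** Exposure and discontinuations are summarised, so a careful reader could see it. Mean exposure does not let that reader correct a first-event percentage. The table specifications sit in a programming plan that was not available, and some SAP text is redacted, so a further summary may exist there.

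**Conclusion.** The point holds in a limited form. The visible SAP text gives adverse events only as crude percentages, defines treatment-emergent events per period without an end date, and places no common time frame on arms whose windows can differ.

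Under equal constant hazards of 0.02 to 0.05 per month and 0 to 50% crossover, the artefact is about 2 to 13 points (A vs B 2.1 to 8.4; A vs C 3.9 to 13.1). At 0.10 per month and 50% crossover it reaches 18.7 for A vs C. Front-loading brings it to about 1 to 5 points at an initial hazard of 0.05. Sufficient toxicity stops in Arm A reverse it.

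These sizes rest on exponential PFS and on assumed hazards, crossover and stop rates, with event risk independent of PFS. They show what could happen and do not predict a direction. The change is worth making because it is cheap and uses dates already collected. It does not call the planned efficacy analyses into question.

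**What to change.** In SAP 3.8.1 to 3.8.3:

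1. Keep the crude counts and percentages.
2. State the end of each treatment-emergent period: the earliest of 90 days after last dose, start of the next treatment period, or start of subsequent anticancer therapy.
3. For any TEAE, Grade ≥3 TEAE, SAE, AESI and AE leading to discontinuation, add by arm the cumulative incidence of first event at 3 and 6 months with confidence intervals. Treat death as a competing event. Say by rule how crossover, reinduction or retreatment ends time at risk. If these are censored, note that they follow progression and may be informative.
4. Base any between-arm safety description for Arms A, B and C on these fixed-time estimates.
5. Show exposure-adjusted rates, if at all, as supportive only, because they mislead when immune events are front-loaded.

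The cost is SAP wording and one extra table. The main drawback is imprecision: with about 26 subjects and 40% incidence the standard error within one arm is √(0.24/26) = 9.6 points, and with about 13 it is 13.6.

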3.8.2 Adverse Events of Special Interest

Some clinical concepts (including some selected individual preferred terms) have been considered “AEs of special interest” (AESI) to the MEDI4736 program. Adverse events of special interest are defined in the protocol section 5.3. The number and frequency of subjects reporting AESI will be summarized.

3.8.3 Deaths and Treatment Discontinuations due to Adverse Events

The number and percentage of subjects reporting treatment-emergent AEs leading to treatment discontinuation and death will also be summarized in a similar format as SAE.

3.8.4 Clinical Laboratory Evaluation

Laboratory tests will be grouped according to hematology, serum chemistry, urinalysis, coagulation, and thyroid function tests (TSH, free T3, and free T4). For all continuous laboratory assessments, absolute value and change from baseline will be summarized for each scheduled assessment, “worst-case” (nadir and/or zenith) on treatment, and the last assessment on-treatment using descriptive statistics.

Laboratory abnormalities with toxicity grades according to the NCI CTCAE 4.03 will be derived according to laboratory values. Frequencies of worst observed Grades, as defined by NCI CTCAE v4.03, will be presented for each laboratory parameter. The analysis will present the rates of subjects with Grade 3-4 toxicity. For each lab parameter, percentages are

calculated based on the number of subjects who have a baseline and at least one post-baseline assessment.

Also, laboratory parameters will be assessed by presenting tables containing information related to 2-grade (or greater) laboratory shifts from baseline.

3.8.5 Other Safety Evaluations

3.8.5.1 Vital Signs

Vital signs will be measured on study days noted in Protocol Section 4.2. Descriptive statistics of baseline value, post-baseline value and change from baseline value for heart rate, blood pressure, temperature, and respiratory rate will be provided for each scheduled assessment including the last assessment on-treatment as well as for the maximum and minimum post-baseline on treatment values.

3.8.5.2 Electrocardiogram

Electrocardiogram parameters (PR, RR, QRS, QT, QT corrected using Fridericia's formula QTcF) will be summarized using descriptive statistics for actual values and for changes from baseline by treatment arm by scheduled time of evaluation including end of treatment visit as well as for the maximum post-baseline values. The QTcF will be considered as the primary correction method to assess subject cardiac safety.

The notable ECG interval values in maximum absolute QTcF intervals (new > 450 milliseconds, new > 480 milliseconds, new > 500 milliseconds) and the maximum absolute uncorrected QT intervals (new > 500 milliseconds) over all post-baseline evaluations, as well as in QTcF maximum changes from baseline (> 30 and > 60 milliseconds) over all post-baseline evaluations will be summarized by treatment. "New" means the category of the QTc abnormality was not present at baseline and became present at least one post-baseline ECG assessment.

3.8.5.3 ECOG Performance Status

ECOG performance status will be summarized using a shift table showing change in ECOG from baseline to the worst performance status on-treatment and to the last assessment on-treatment.

3.8.6 Subgroup Analyses

Not applicable.

[Redacted text block]

[Redacted text block]

[Redacted text block]

6 APPENDIX

Table A. Statistical Analysis Plan Amendments

SAP Version	Date	Key Details of Amendment	Reason for Amendment
1.0	23MAR2016	Initial document	Initial document
2.0	18MAY2017	
 Added the sample size calculation for the new Arm E (Section 2.4.2) Analyses related to the new Arm E and some clarifications added in the efficacy analysis section (Section 3.4) 	
 To be aligned with protocol language
2.1	17APRIL2019	
 Correct exact and standard confidence intervals for ORR and PFS (Section 2.4.2) Inclusion of Arm E in the definition of OR. Correction of duration of non-treatment interval following 3 missed doses (Section 3.4.1) Inclusion of Arm E in definition of secondary efficacy endpoints. Correct method of assignment of Arm E cohort (Section 3.4.2) Correct method of assignment of Arm E cohort. Include missing multiple-item axis and single item STO22 scores for EORTC (Section 3.5.1) Editorial changes for clarity (multiple sections) 	
 Insure methods completeness for CSR development To be aligned with protocol language To be aligned with protocol language To be aligned with protocol language and EORTC scoring methodology To insure proper presentation of final CSR TFLs
3.0	15MAY2019	
 Remove multiple-item STOANX endpoint and STO22 single item endpoints from QoL summaries 	
 No clinical meaningfulness for these endpoints.
